3.1 Primary objective

To evaluate the efficacy of a Esflurbiprofen 165 mg Hydrogel Patch applied once a day compared with placebo in patients with acute blunt, soft tissue injuries of the limbs.

Teikoku Chemical Co. Ltd Clinical Study Protocol : TK-254R-0201 Confidential Final Version 3.0

- □ The primary efficacy outcome is pain-on-movement (POM) change from baseline assessed by Visual Analogue Scale (VAS) to Visit 5 (72 hours after initiating treatment).
- □ Important secondary efficacy outcomes are POM on VAS at Visit 2, 3, 4, 6 and 7 (12, 24, 48, 96 and 168 hours after initiating treatment).

3.2 Secondary objective

To assess the safety of Esflurbiprofen Hydrogel Patch compared with placebo applied once a day for up to seven days.

4 Study design

This is a Phase II randomized, double-blind, 2-arm (1:1) (stratified by center and subgroup), multi-center, placebo-controlled, parallel group study of the efficacy and safety of Esflurbiprofen Hydrogel Patch applied once a day for up to 8 days (maximum of 7 patches) to treat acute blunt, soft tissue injuries of the limbs.

To qualify, patients must experience acute blunt, soft tissue injuries of the limbs. Patients should be randomized as soon as possible after the injury. Anticipated time from injury until initial treatment should not exceed 6 hours.

In order to ensure at least 90 evaluable patients per group, up to 200 patients (100 in each group)

Approximately 200 patients suffering from acute blunt, soft tissue injuries of the limbs are to be randomized to be treated with Esflurbiprofen Hydrogel Patch or placebo (assumes a drop-out-rate of $\leq 10\%$).

The study will be performed in Germany in 3 sites. Each site should enroll a minimum of 30 and a maximum of 90 patients.

The first five doses of study drug will be applied at the study site. The patients will be instructed on how to apply the patch once daily at home for the last two treatment days.

After the randomization visit (V1), patients will return to the study center for post-baseline visits V2-V7 to complete efficacy and safety assessments. In addition, patients will assess pain on movement and spontaneous pain intensity at rest at visits 2, 3, 4, 5, 6 and 7.

The schedule of visits is described below.

	Time after initiating treatment	Visit Day
Randomization/Baseline visit V1	0 h	Day 1
1st interim visit V2	12 h (□ 1 h) after V1	Day 1
2nd interim visit V3	24 h (□ 2 h) after V1	Day 2
3rd interim visit V4	48 h (□ 4 h) after V1	Day 3

Table 4–1: Study site visits

Teikoku Chemical Co. Ltd Clinical Study Protocol : TK-254R-0201 Confidential Final Version 3.0

4th interim visit V5	72h (□ 4 h) after V1	Day 4
5th interim visit V6	96 h (□ 4 h) after V1	Day 5
Final visit V7	168 h (□ 24 h) after V1	Day 8 🗆 2day

Rescue medication (paracetamol, 500 mg tablets, up to 3000 mg daily) is allowed during the study, except for the 6 hours prior to V5 (72h).

5 Population

The study population will consist of male or female patients aged 18-60 years with blunt, soft tissue injuries of the limbs.

5.1 Inclusion criteria

Patients eligible for inclusion in this study must fulfill all of the following criteria: The following must apply:

- 1. acute sports-related soft-tissue injury/contusion (strains, sprains, bruises) of the upper or lower limb
- 2. location of injury such that pain-on-movement (POM) is elicited on by the exercises described in Section 7.5
- 3. enrollment within 6 hours of the injury
- 4. baseline VAS score for POM of injured extremity \geq 50 mm on a 100 mm VAS
- 5. size of injury, as assessed by investigator, $\geq 25 \text{ cm}^2$ and $\leq 120 \text{ cm}^2$
- 6. adult male or female patients
- 7. age 18 to 60 years
- 8. having given written informed consent
- 9. satisfactory health as determined by the Investigator based on medical history and physical examination.

5.2 Exclusion criteria

Patients eligible for inclusion in this study must not fulfill any of the following criteria:

- 1. significant concomitant injury in association with the index acute sports-related softtissue injury/contusion; e.g. fracture, nerve injury, ligament disruption, tear of muscle or cartilage, or open wound
- 2. excessively hairy skin at application site, cutting the hair in the injured site prior to patch application will qualify for inclusion
- 3. current skin disorder or shaving hair at application site
- 4. history of excessive sweating/hyperhidrosis inclusive of application site
- 5. intake of NSAIDs or analgesics within 36 hours, opioids within 7 days, or corticosteroids within 60 days of inclusion in the study
- 6. intake of long-acting NSAIDs or application of topical medication since the injury (RICE allowed)

- 7. participation in a clinical study within 30 days before inclusion in the study or concomitantly
- 8. drug or alcohol abuse in the opinion of the investigator
- 9. Pregnant and lactating women
- 10. Women of child-bearing potential (defined as all women physiologically capable of becoming pregnant) who are not using an acceptable method of contraception defined as:
- □ Surgical sterilization
- □ Hormonal contraception
- □ IUD
- □ Double barrier method
- □ Total abstinence throughout the study at the discretion of the Investigator.

Periodic abstinence is NOT an acceptable method of contraception. An acceptable method of contraception must be maintained throughout the study.

A woman who is post-menopausal must have a negative urine pregnancy test at screening but will not need to comply with an acceptable method of contraception. Women are considered post-menopausal and not of child bearing potential if they had 12 months of natural (spontaneous) amenorrhea with an appropriate clinical profile (e.g. age appropriate, history of vasomotor symptoms) or six months of spontaneous amenorrhea with serum FSH levels > 40 mIU/mL or have had surgical bilateral oophorectomy (with or without hysterectomy) at least six weeks ago. In the case of oophorectomy alone, only when the reproductive status of the woman has been confirmed by follow up hormone level assessment.

- 11. known hypersensitivity to Esflurbiprofen or one of the excipients of the patch
- 12. patients with any ongoing condition that may interfere with the absorption, distribution, metabolism, or excretion of Esflurbiprofen
- 13. history of previous significant injury to the same extremity within 6 months
- 14. patients with a disease affecting the same limb, such as synovitis, rheumatoid arthritis, arthrosis, etc.
- 15. patients having an ongoing painful condition associated with sports-related injury/contusion
- 16. patients suffering from symptoms of an infectious disease including swelling of any joint of the affected upper or lower limbs
- 17. patients who had surgery of the affected upper or lower limb within one year of study entry
- 18. patients with significant diseases (defined as a disease which, in the opinion of the investigator, may either put the patient at risk because of participation in the study or a disease which may influence the results of the study or the patient's ability to participate

in the study; includes patients with a history of gastrointestinal bleeding, significant cardiovascular, liver or renal disease).

- 19. patients with a blood coagulation disorder
- 20. patients who use any impermissible medication (section 6.5.6)

6 Treatment

6.1 Investigational drug and reference drugs

CLINSEARCH will supply the study drugs and rescue medication (section 6.5.5).

Study drugs will be packed and labelled by CSM, Clinical Supplies Management Europe GmbH.

Esflurbiprofen Hydrogel Patch and the placebo patches are packaged in

. One sachet contains 1 plaster.

The number of IMP units to be packaged will be specified prior to the start of the packaging operations, including units necessary for carrying out quality control and any retention samples to be kept.

The clinical trial supplies will be packed into secondary containers (boxes). Supplies for replacements will be packed separately into further secondary containers.

The IMPs will be labelled in accordance with the GMP Annex 13 and with the GCP regulation ("GCP-Verordnung") § 5.

Investigational drug:

- Active ingredient: Esflurbiprofen Hydrogel Patch containing 165 mg Esflurbiprofen
- □ Excipients:

One unit dose of the drug is one patch applied to the painful area.

Control drug:

Placebo patch that does not contain the active ingredient but is otherwise indistinguishable from the investigational drug Esflurbiprofen Hydrogel Patch.

Rescue medication:

Paracetamol (500 mg tablets, up to 3000 mg daily) is allowed during the study, except for the 6 hours prior to Visit 5 (72h).

6.2 Treatment arms.

Eligible patients will be randomized to one of two treatment arms in a ratio of 1:1

- Esflurbiprofen Hydrogel Patch once a day
- \Box Placebo patch once a day

6.3 Treatment assignment

At Visit 1, all patients who fulfill all the inclusion/exclusion criteria will be given the lowest available number on the randomization list. This number assigns them to one of the treatment arms. The Investigator or designee will enter the randomization number on the CRF.

The randomization numbers will be generated using the following procedure to ensure that treatment assignment is unbiased and concealed from patients and investigator staff. A randomization list – stratified by center and subgroup - will be produced by the independent statistician **stratistic statistic st**

Randomization data are kept strictly confidential by CRMB and the packaging company, accessible only to authorized persons, until the time of unblinding. At the conclusion of the study, the occurrence of any emergency code breaks will be determined after return of all code break reports and unused drug supplies to the packaging company. Only when the study has been completed, the database locked, and the Statistical Analysis Plan finalized will the drug codes be broken and made available for data analysis.

6.4 Treatment blinding

The study will be double-blind. Patients, investigator staff, persons performing the assessments, monitors and data analysts will remain blinded to the identity of the treatment from the time of randomization until database lock, using the following methods: (1) Randomization data are kept strictly confidential, accessible only to authorized persons, until the time of unblinding. (2) the identity of the treatments will be concealed by the use of study drugs that are all identical in packaging, labeling, schedule of administration, appearance and odor.

Unblinding will only occur in the case of patient emergencies (see section 6.5.10) and at the conclusion of the study.

6.5 Treating the patient

6.5.1 Patient numbering

Each patient is uniquely identified in the study by a randomization number, i.e. a combination of the center number and patient number. A center number is assigned by the packaging company to each investigative site. At Visit 1, each patient who qualifies for randomization will be given the lowest patient number available at the center. The Investigator or designee will enter the randomization number on the CRF. Once assigned to a patient, a randomization number will not be re-used.

6.5.2 Dispensing the study drug

Each of the investigator sites (study centers) will be supplied by the packaging company with study drug in packaging of identical appearance.

The study medication packaging has a 2-part label. A unique randomization number is printed on each part of this label which corresponds to a treatment arm (active or placebo patch), according to the confidential randomization list. Immediately before dispensing study drug to the patient, investigator staff will detach the outer part of the label from the packaging, and affix it to the patient's CRF.

6.5.3 Study drug supply, storage and tracking

Study drug must be received by a designated person at each study center, handled and stored safely and properly, and kept in a secured location to which only the Investigator and designated assistants have access. All study drugs should be stored according to the instructions specified on the drug label. The patches must be stored at room temperature (15-30C). Clinical supplies are to be dispensed only in accordance with the protocol.

Medication labels will be in the local language (German) and comply with the legal requirements of the Germany. They will include storage conditions for the drug, but no information about the patient except for the randomization number.

The Investigator or designee must maintain an accurate record of the shipment and dispensing of study drug in a drug accountability ledger. Drug accountability will be monitored by the study monitor during monitoring visits and at the completion of the study. Patients will be asked to return all used and unused study drug and packaging at the end of the study or at the time of discontinuation.

At the conclusion of the study, and as appropriate during the course of the study, the Investigator will return all used and unused study drug, packaging, drug labels, and a copy of the completed drug accountability ledger to the Clinsearch monitor or to the Clinsearch address provided in the investigator folder at each site.

6.5.4 Instructions for prescribing and taking the study drug

All patients will be treated with 1 patch of study drug at every visit during the first 6 visits (except for visit 2). The first five patches will be applied at the study center. The site of the first application will be marked with a water-resistant pen to ensure the same application site at every treatment. Additional 3 patches will be dispensed at Visit 6. The patients will be instructed to apply one patch every day at approx. the same time. Dosing times should be distributed as evenly as possible, preferably once every 24 hours after the last application.

Patients can take a shower or bathe prior to the application.

The Investigator or study staff will instruct the patients to apply the study drug exactly as prescribed and state that compliance is necessary for the patients' safety and the validity of the study. The patients will be told to contact the Investigator or study staff if they are unable for any reason to apply the patch as prescribed. All dosages prescribed and dispensed to the patient

and all dose changes during the study must be recorded on the Dosage Administration Record CRF page.

If the hydrogel patch begins to peel-off (>10% of the total surface), the edges of the topical system may be pressed down. If problems with adhesion persist, patients may overlay the topical system with a mesh netting sleeve, where appropriate (e.g., to secure topical systems applied to ankles, knees, or elbows). The mesh netting sleeve must allow air to pass through and not be occlusive (non-breathable)

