Use of systemic or topical NSAIDs, analgesics (other than paracetamol), opioids, corticosteroids (except for topical treatment of bronchial asthma), heparin, or psychotropic agents, as well as the use of adhesive and fixing tapes and casts that would jeopardize the assessment of the primary variable (pain on movement).

3. Other treatments

. Ultrasound, physical therapy and acupuncture will not be allowed

Dosage Patients will be randomly assigned to one of the following treatment arms in a ratio of 1:1.

A: Esflurbiprofen Hydrogel Patch applied once per day to the affected injury site

B: Placebo patch applied once per day to the affected injury site

The dose regimen is a single hydrogel patch (investigational drug) applied topically to the injured site once a day for 7 days. The hydrogel patch should be positioned directly over the injury site and marked with a water-resistant pen to ensure the patch is applied at the same site throughout the study. The placebo patch (placebo) is identical in composition to the Esflurbiprofen 165 mg Hydrogel Patch, without the active ingredient. Placebo is applied as described for the investigational drug. Both patients and investigators will be blinded to study treatment. If the hydrogel patch begins to peel-off (>10% of the total surface), the edges of the topical system may be pressed down. If problems with adhesion persist, patients may overlay the topical systems applied to ankles, knees, or elbows). The mesh netting sleeve must allow air to pass through and not be occlusive (non-breathable)

Teikoku Chemical Co. Clinical Study Protocol	Ltd : TK-254R-0201	Confidential Final Version 3.0	Page 14
No. of Visits	A total of 7 visits		
Visit Schedule	 Visit 1 of Visit 2 of Visit 3 of Visit 4 of Visit 5 of Visit 6 of Visit 7 of 	n Day 1 (enrollment) n Day 1/2, depending on am/ n Day 2 (24 hours) n Day 3 (48 hours) n Day 4 (72 hours) n Day 5 (96 hours) n Day 8 (168 hours).	pm enrollment (12 hours)
Assessments	Efficacy will be a	assessed based on the followi	ng:
	 Primary assessme Pain-on-move standardized = 12, 24, 48, 72 Secondary assess AUC over time 	ent: cment (POM) measured by 10 movements as described in S d, 96 and 168 hours ments: me between baseline and the	00 mm VAS [performing ection 7.5.1] at baseline, first 12, 24, 48, 72, 96 and

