Teikoku Chemical Co. Ltd Clinical Study Protocol : TK-254R-0201

Documentation of use of rescue medication, if needed (diary check).

- \square Record changes in the use of concomitant medication (section 6.5.6).
- \square Record information on AEs (section 8.1).
- \Box Spontaneous pain intensity, pain at rest (PAR) (section 7.5.1)
- \Box Injury site pain-on-movement (POM) (section 7.5.1).
- □ Visit 4: Global efficacy assessments (GEA) by patient and investigator (section 7.5.1).
- \Box Adhesive power of patch (section 7.5.1).
- □ Local tolerability assessment (except V2).

Visit 5 (72h \pm 4 h)

- \Box Apply next dose of study medication.
- □ Count used/unused patches & collect used patches.
- □ Check for last intake of rescue medication no later than 6 hours prior to Visit.
- □ Documentation of use of rescue medication
- \square Record changes in the use of concomitant medication (section 6.5.6).
- \square Record information on AEs (section 8.1).
- □ Spontaneous pain intensity, pain at rest (PAR) (section 7.5.1)
- \Box Injury site pain-on-movement (POM) (section 7.5.1).
- \Box Global efficacy assessments (GEA) by patient and investigator (section 7.5.1).
- Responder rate 1 (number of patients achieving 50% reduction from baseline in the VAS score for POM)
- \Box Adhesive power of patch (section 7.5.1).
- □ Local tolerability assessment.

Visit 6 (96h+4h)

- □ Apply next dose of study medication.
- □ Count used/unused patches and collect used patches.
- \Box Use of rescue medication.
- \square Record changes in the use of concomitant medication (section 6.5.6).
- \square Record information on AEs (section 8.1).
- \Box Spontaneous pain intensity, pain at rest (PAR) (section 7.5.1).
- \Box Injury site pain-on-movement (POM) (section 7.5.1).

- \Box Adhesive power of patch (section 7.5.1).
- □ Local tolerability assessment.
- □ Dispense patient card (section 6.5.7) and diary (section 6.5.8) and instruct patient about appropriate use.
- Dispense three patches to the patient.
- \Box The patient is instructed on the method and time of application of study drug (section 6.5.4).

Visit 7 (Day 8 ± 2 days) - Final visit

Procedures for this visit are also to be completed if the patient terminates the study prematurely.

- \Box Count used/unused patches and collect used patches.
- \square Record changes in the use of concomitant medication (section 6.5.6).
- \Box Record information on AEs (section 8.1).

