¹ Female patients only; ² Patients will be given pouch containing IMP to take home in case of need to replace a detached patch. Patients bring IMP with them to each subsequent clinic visit. Patient apply patches themselves at 120h and 144h. ³ A final visit will be							

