14.13 Treatment compliance, rescue medication, other concomitant therapies

Compliance is defined in terms of the total number of study medication patches used and total number of applications made through Visit 7 as follows:

- Good: > 80% of the patch has been applied and > 80% of scheduled applications made,
- Moderate: not Good and not Poor
- Poor: < 50% of the patch has been applied or < 50% of scheduled applications made.

Compliance in patients with missing data on patch counts will be documented in the Blind review meeting before unblinding.

The % of patch used through Visit 7 will be computed relative to the actual number of applications made from randomization through Visit 7. Scheduled applications will include all scheduled applications through Visit 7.

CRMB	Trial Substance:	Esflurbiprofen Hydrogel Patch	Study No.: EudraCT No.:	TK-254R-0201 2020-005165-14
	Short Title:	Local symptomatic and short-term treatment of pain in acute strains, sprains or bruises of the extremities following blunt trauma		DKU SEIYAKU CO LTD.

Compliance will be summarized descriptively as (1) % of scheduled applications made, (2) % of patches used relative to number of actual applications and (3) compliance category (Good/Moderate/Poor).

Use of concomitant therapies will be listed. Use of rescue medication is an efficacy outcome and is discussed further below. Exposure to study drug will be summarized descriptively as (1) number of applications made and (2) total amount of patch used.

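### Three patches are dispensed at Visit 6 with an instruction to apply one daily, but only two home applications are scheduled, so a patient with a late Visit 7 could apply 8 patches against a stated maximum of 7

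*Protocol*

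**What the plan says.** **Two home applications, seven patches in all.** The Protocol synopsis gives the regimen as one patch "applied topically to the injured site once a day for 7 days". Section 4 (Study design) describes a patch "applied once a day for up to 8 days (maximum of 7 patches", with the first five doses applied at the site and patients then instructed to "apply the patch once daily at home for the last two treatment days". Footnote 2 to Table 7-1 fixes the times: "Patient apply patches themselves at 120h and 144h". The SAP repeats this footnote under its schedule of assessments (5.5.1).

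**Three patches for home, one a day.** Section 6.5.4 states: "Additional 3 patches will be dispensed at Visit 6. The patients will be instructed to apply one patch every day". The Visit 6 list in section 7 agrees on the number: "Dispense three patches to the patient". Section 6.5.4 prefers a 24 h interval from the previous application and gives no time for the last one.

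**Replacement patches.** Footnote 2 also says that patients take home a pouch of study drug in case a patch detaches. It is attached to a Table 7-1 row for dispensing study drug, marked at Visits 1 and 6. The three patches at Visit 6 have a separate row without a footnote.

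**Compliance.** Protocol 9.6 and SAP 14.13 define the denominator thus: "Scheduled applications will include all scheduled applications through Visit 7". No number is given.

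**The concern.** Section 6.5.4 is the working instruction on how patients use the patch. It links three dispensed patches directly to daily application. A patient who obeys it, and whose final visit is not early, has no reason to stop at two. The same protocol sets a maximum that this patient would pass.

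Two things are at stake. First, the number of doses would depend on when Visit 7 is booked and on which passage the site read out, and some patients could exceed the protocol's own limit. Second, Visit 7 collects pain, adhesion and local tolerability scores. Adhesion and skin reaction depend on how long ago the last patch was applied, and that interval would differ between patients following different passages.

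**Working it through.** **Inputs.** Site applications at 0, 24, 48, 72 and 96 h: 5 (6.5.4 and Table 7-1, none at Visit 2). Scheduled home applications at 120 h and 144 h: 2 (footnote 2). Dispensed for home at Visit 6: 3. Interval: 24 h.

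**The plan's own figure.** 5 + 2 = 7, which equals the stated maximum in section 4.

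**Visit 7 windows.** Table 4-1 and SAP section 3 give 168 h ± 24 h and, beside it, Day 8 ± 2 days. Table 7-1 gives 7 days ± 2 days, on Day 7, 8 or 9. SAP 5.5.1 and section 15 give 7 days ± 1 day. The mapping rule in Protocol 9.4 and SAP 14.2 takes 168 h onward. A visit between 168 h and 192 h lies inside all of them; 216 h lies only inside the ± 2 day versions.

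**Count under each reading.** Literal 6.5.4 means one home patch every 24 h from 120 h until the visit, limited to the 3 dispensed. A patch falling due exactly at the visit is not counted.

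| Visit 7 at | Patches, 120 h/144 h schedule | Patches, literal 6.5.4 | Hours since last patch, schedule | Hours since last patch, literal 6.5.4 |
|---|---|---|---|---|
| 144 h | 5 + 1 = 6 | 5 + 1 = 6 | 144 − 120 = 24 | 24 |
| 168 h | 5 + 2 = 7 | 5 + 2 = 7 | 168 − 144 = 24 | 24 |
| 172 h | 7 | 5 + 3 = 8 | 172 − 144 = 28 | 172 − 168 = 4 |
| 192 h | 7 | 8 | 192 − 144 = 48 | 192 − 168 = 24 |
| 216 h | 7 | 8 | 216 − 144 = 72 | 216 − 168 = 48 |

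The readings part only after the 168 h dosing time. That threshold is approximate: Visit 6 may take place at 92 h (96 h − 4 h), and 24 h steps from there fall at 116, 140 and 164 h, which puts the eighth patch before an on-time 168 h visit.

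**Compliance.** Only seven applications are scheduled, so the denominator is 7 for any Visit 7 after 144 h. Eight applications score 8/7 = 114.3%. The Good category has no upper limit, so this patient would be graded Good and the overuse would not show in the category.

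**The case against.** The strongest reply is that the plan already fixes the dose count. The synopsis, section 4, footnote 2 and the SAP copy of that footnote all point to seven, and one patch a day in 6.5.4 can be read as a frequency rather than a duration. Dispensing three does not contradict applying two: unused patches must be returned, so leftovers are expected, and a replacement patch is provided for. Footnote 2 covers both the replacement pouch and the 120 h/144 h doses, so the two Table 7-1 rows may describe one dispensing of two doses and a spare.

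This stands as a plausible account of the intent. It does not remove the conflict. No passage calls the third patch a spare or says whether a replacement counts toward the maximum, and 6.5.4 is the section that tells patients what to do.

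The reply also notes that the diary and patch counts would reveal overuse, that the number of applications is summarised, and that deviations go to blind review. That is true, but an eighth patch applied under 6.5.4 is not clearly a deviation until it is settled which passage governs.

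Three stronger readings are tempting and are not supported:

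- **A compliance denominator of 8.** A reader might infer that six applications fall from 6/7 = 85.7% (Good) to 6/8 = 75.0% (Moderate). That counts an unscheduled patch as scheduled. A third home patch can raise the numerator, not the denominator.
- **Damage to the main result.** The primary endpoint is at 72 h and the discrepancy begins after 96 h. The instruction is the same in both blinded arms, secondary tests are exploratory, and compliance is descriptive. No between-arm bias is shown.
- **Nine patches.** Daily use to 216 h would make a fourth home patch due at 192 h, but only three are dispensed for daily use, and 216 h is not inside every window.

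**Conclusion.** The passages conflict on home applications, and the conflict sits in an operative instruction. Its size is one patch: 8 against a stated maximum of 7, for patients who use the third patch as a daily dose and have Visit 7 after about 168 h. A visit of that kind is within plan up to 192 h under every window. For these patients, the interval from last patch to the Visit 7 adhesion and skin scores differs by 24 h between the two readings (4 h or 28 h at a 172 h visit, 24 h or 48 h at 192 h).

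The conclusion rests on two assumptions: that 6.5.4 is followed as written, and that patches in the replacement pouch are not used as daily doses. How many patients would be affected cannot be estimated from the documents. With Visit 6 at 96 h and Visit 7 at 168 h or earlier, both readings give at most 7. The point deserves correction because it governs what patients are told to do; it does not threaten the primary analysis.

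**What to change.** **Protocol.** Reconcile section 6.5.4, the Visit 6 list and Table 7-1 with section 4, so that the number of home applications and the time of the last one are the same everywhere. State what any additional dispensed patch is for and whether a replacement counts toward the maximum. The number is the sponsor's decision. Carry the result into the patient instructions.

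**SAP 14.13.** Count as scheduled only the applications due by the patient's own last visit under the reconciled schedule. A single fixed denominator for everyone should be avoided: a patient whose last visit falls after the 48 h patch and before the 72 h one has had 3 of 3 due, yet would score 3/7 = 42.9% and be graded Poor. Add a table, by arm, of patients above the stated maximum.

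**Cost.** Protocol wording, a line in the patient instructions, an SAP sentence and one table. Application times are already in the diary and patch counts in the CRF, so no further data or patients are needed. If home dosing is already complete, the SAP change can still be made before unblinding.
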